2. GLOSSARY

ABC	Area under the curve
AINE	Non-steroid anti-inflammatory
BAK	Benzalkonium chloride
Cmax	Maximum concentration
COX1	Cyclooxygenase 1
COX2	Cyclooxygenase 2
FDA	Food and Drug Administration
HFB	Hydroxyfluoroprednisolone
PGE2	Prostaglandin E2
PIO	Intraocular pressure
T1/2	Half life
Tmax	Time to reach the maximum concentration
OSDI	Ocular Surface Disease Index
TRL	Tear film breakup time
mmHg	Millimeter of mercury
FRC	Case report form
UV rays	Ultraviolet rays
LOCS III	Lens Opacities Classification System

3. BACKGROUND

The manipulation of the ocular structures during surgery, infectious phenomena, trauma in the ocular globe, allergies, etc., are events that cause an inflammatory cascade, due to the release of a large number of chemical mediators, after cell lysis, and induce the expression of cyclooxygenase 1 and 2 (COX1 and 2). The COX-2 products are prostaglandins, which have different effects on the damaged tissue (see figure 1).

[figure not shown]

Figure 1. The loss of integrity of the cellular membrane as consequence of the surgical manipulation of the ocular structures causes an increase in the bioavailability of membrane phospholipids, which are biotransformed by phospholipases into arachidonic acid. 5-lipoxygenase acts on the arachidonic acid and synthesizes leukotrienes, which increase the vascular permeability and vasoconstriction. Cyclooxygenases, upon acting on the arachidonic acid, synthesize prostaglandins and thromboxanes, which

Prostaglandins cause the filtration of fluid from the perifoveal capillary networks to the extracellular space of the macular region. Some of the main ocular signs and symptoms in which prostaglandins have been involved are inflammation, pain, conjunctival hyperemia, posterior synechiae, opacity of the posterior capsule, changes in ocular tension, glaucoma, and cystic macular edema.

Considering the role taken on by the inflammation in the development of this process, the use of two groups of drugs to prevent the deteriorating effects of its onset has been proposed:

1. Non-steroid anti-inflammatory agents that directly inhibit COX1 and COX2 enzymes.
2. Topical corticoids that act on the A2 phospholipase level, inhibiting the release of prostaglandins.

Non-steroid anti-inflammatories present higher safety in chronic dosing schedules compared to corticoid anti-inflammatories; however, in terms of anti-inflammatory potency they are superior to the latter.

Currently, there are four FDA-approved ophthalmic AINES for treatment of inflammation following cataract surgery: diclofenac 0.1 % solution, ketorolac 0.5 % suspension, nepafenac 0.1 % suspension, and bromfenac 0.09 % solution. Bromfenac is a non-steroid anti-inflammatory byproduct of phenylacetic acid related to diclofenac. Its unique chemical structure confers high lipophilicity, quick penetration, and higher immediate and sustained bioavailability in all ocular tissue.¹

Bromfenac 0.9 mg/ mL eyewash is intended for treating post-surgery ocular inflammation after the extraction of cataracts in adults, based on good preclinical and clinical results.

The ophthalmic bromfenac 0.09 % solution has demonstrated its safety and efficacy as a topical ocular AINE, specifically, in a controlled inflammation model such as surgical trauma in the anterior chamber (phacoemulsification); said study demonstrated its efficacy in reducing the swelling of different structures in the post-surgery period, such as corneal edema, conjunctival hyperemia, chemosis, intracameral cellularity, and retinal edema.²

In comparison with other AINES available on the market, it was also demonstrated that its efficacy is similar and its tolerability is satisfactory as well as its safety.

Currently, thanks to the diversity of available drug products for the treatment of ocular inflammation, we as ophthalmologists can be more precise in the treatment scheme granted to the subject; that is to say, we can choose, depending on the gravity of the inflammatory symptoms, the anti-inflammatory with the desired effect and the lowest number of possible adverse events.

Chronic pathologies with an inflammatory component, such as Pterygium, occur with recurrent aggravations in which symptoms and signs that, while they may not permanently affect the structure of the eye, do diminish the visual quality, are exacerbated.

The ideal AINE is that which reaches therapeutic concentrations in the anterior and posterior segment levels, has an excellent anti-inflammatory activity, is analgesic, safe, and well-tolerated. Different types of AINES are formulated and sold for their use in ophthalmology: indomethacin 1 %, diclofenac 0.1 %, ketorolac 0.5 %, nepafenac 0.1 %, and bromfenac 0.09 %; among these the most innovative are nepafenac and bromfenac. All are organic acids except nepafenac, which is an amide analog and is formulated as a suspension instead of a solution. All of them reach therapeutic concentrations in the aqueous humor, iris, and ciliary body. However, most are not able to reach the posterior pole. Only the next-generation AINES – bromfenac and nepafenac – are able to reach therapeutic concentrations in the posterior segment and are the most inhibitory for COX2, which has the highest expression at the retina level.

4. JUSTIFICATION

Steroids are considered the “golden standard” for treating inflammation and may cause multiple adverse events such as: increase in intraocular pressure, susceptibility to infection, delay in the healing of corneal injuries, glaucoma, and posterior subcapsular cataracts, among others; for which reason AINEs represent a safer alternative for the treatment of long-term post-surgery inflammation.

Most AINEs are weak acids and are ionized with the tear pH, limiting their permeability towards the anionic cornea. Due to their pharmacological characteristics, AINES must be combined with insoluble cationically-charged complexes, as is the case with benzalkonium chloride, to facilitate their penetration and solubility.

Currently, four topical non-steroid anti-inflammatories are approved by the Food and Drug Administration (FDA) for the treatment of inflammation: diclofenac 0.1 %, ketorolac 0.5 %, nepafenac 0.1 %, and bromfenac 0.09 %. Of these, bromfenac is the only one approved at a dosage of twice a day and which is currently used to treat post-surgery inflammation, blepharitis, conjunctivitis, and escleritis.³

The use of topical ocular AINES was limited to their chronic use, which also presents adverse events such as corneal abrasion, tear film dysfunction, or even corneal melting. Recent evidence regarding bromfenac being used for 3 weeks indicates that its dosage of twice a day appears to be safe for the ocular surface.

There is a report by Frucht J, et al. which compares the use of indomethacin 0.1 % versus dexamethasone 0.1 % to handle ocular signs and symptoms associated with Pterygium and Pinguecula, under a dosing schedule of 1 drop 6 times a day for 3 days, followed by 1 drop 4 times a day for 11 days for both drug products.

Although the authors assert that both drug products are efficient and safe, the dosing schedule entails the frequent administration of the drug products, which represents an increase in the risk of the subject's failure to follow the treatment, for which reason we propose bromfenac as a useful drug in the control of clinical signs such as hyperemia in an inflammatory disease model that requires a drug with less adverse events and a lower frequency of administration than other AINES.⁴

5. PURPOSES

5.1 General purpose:

Evaluate the efficacy and safety of Zebesten ® (bromfenac 0.09 %) ophthalmic solution in the treatment of conjunctival hyperemia and ocular surface inflammation in a clinical grade I to III Pterygium model.

5.1.1 Specific purpose 1:

Evaluate the efficacy of Zebesten ® in the control of conjunctival hyperemia in subjects with Pterygium through its qualitative assessment through the validated analogous scale of the cornea unit and contact lenses of the University of South Wales.⁵

5.1.2 Specific objective 2:

Evaluate the safety of Zebesten ® through the evaluation of the corneal and conjunctival epithelium through fluorescein and lissamine green staining, the measurement of intraocular pressure, and the Tear film breakup time.

6. SUMMARY

Drug Product Code:	PRO155
Study Drug:	BROMPHENAC 0.09 % OPHTHALMIC SOLUTION
Therapeutic Indication:	Ocular non-steroid anti-inflammatory
Protocol Code:	SOPH155-0415/IV
Sponsor:	Laboratorios Sophia, S.A. de C.V.
Version:	2
Date:	June 2016
Study Title:	Evaluation of the efficacy and safety of Zebesten ® (Bromfenac 0.09 %) ophthalmic solution on the treatment of conjunctival hyperemia and inflammation of the ocular surface in a clinical grade I-III Pterygium model
Study Design:	Controlled, randomized, double blind, masked clinical study, comparing the safety and efficacy of Zebesten ® for the treatment of conjunctival hyperemia in grade I to III Pterygium compared to placebo
Variables to Evaluate:	
Primary outcome
 
 - Conjunctival hyperemia - Tear film breakup time - Adverse events 
Secondary outcome
 
 - Ocular symptomatology 
 o Burning sensation o Foreign body sensation o Photophobia - OSDI questionnaire scoring - Evaluation of epithelial defects with fluorescent dye (cornea and conjunctival) - Evaluation of epithelial defects with lissamine green dye (cornea and conjunctival) - Visual capacity - Intraocular pressure
Groups	
Subjects diagnosed with grade I to III Pterygium will be included in 2 study groups.
 
Group 1 will receive Zebesten ® ophthalmic solution together with Na hyaluronate.
 
Group 2 will receive placebo plus Na hyaluronate.

7. MATERIALS AND METHODS

7.1 Study design

Multicentric, controlled, randomized, double blind clinical study, which compares the safety and efficacy of Zebesten® for the treatment of conjunctival hyperemia in grade I to III Pterygium compared to placebo.

7.2 Sample

The total population will be 166 cases, which will be randomly included and distributed in 2 study groups. Both with diagnosis of grade I to III Pterygium.

Subjects with bilateral Pterygium, in which both eyes meet the selection criteria, can participate with both eyes, taking each eye as one case.

Group 1 will receive Zebesten® ophthalmic solution together with Na hyaluronate.

Group 2 will receive placebo (formulation with no drug substance) together with Na hyaluronate.

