7.3 Blinding

The double blind study is a procedure in which the subject and treating physician do not know which study subjects were assigned to which treatment group. To achieve blind conditions for the drug product, the investigational drug product and the placebo are both packaged in identical bottles with the same legends on the label. The blinding codes are kept by an individual uninvolved in the study designated by the sponsor. The codes are also available in the research center (completely sealed), so the Researcher may refer to them should a subject present a serious adverse event, after being authorized by the study sponsor. The blind conditions are strictly upheld during the data analysis.

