7.5 Distribution into treatment groups

The subjects are distributed into the study groups on the visit indicated in the study timetable, through simple 1:1 randomization, closed envelope technique, through a specialized software that uses random number tables to achieve a uniform distribution in each of the treatment groups.

[figure not shown]

Fig. 1. DISTRIBUTION OF STUDY SUBJECTS. Shows the randomized distribution of the study subjects in the research protocol using a computing system through the closed envelope technique.

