12.4 SAMPLE SIZE CALCULATION

Sample size protocol SOPH155-0415/IV

According to the objectives of the study to evaluate the Zebesten ® effect in subjects with primary pterygium, the variables of primary outcome stipulated in the design were:

- Conjunctival hyperemia
- TRL

Both variables are considered, using similar literature, to perform the calculation of the sample size to meet with the study objectives.

Conjunctival hyperemia

The sample size was calculated according to the formula for the continuous quantitative variables:

$$n = 2 \frac{(Z_{\alpha/2} - Z_{\beta})(\delta)}{d^2}$$

With a statistical trust of 95% that corresponds to the type I error, and is the same as 1.96, with a potency of 80% that corresponds to the type II error, and equals to 0.84. It is considered as a standard deviation for the increase of 0.4 degrees of severity1 in the scale of conjunctival hyperemia after a pterygium surgery, with an expected difference of at least 2.9 degrees of severity.

Based on the previous the result was 69 cases (eyes) per group, which was incremented 20% by consideration of the losses (14 subjects), with **a total of 83 cases per group**, with a total population of study of **166 eyes to treat**.⁸

Tear film breakup time

The sample size was calculated according to the formula for continuous quantitative variables:

$$n = 2 \frac{(Z \propto -Z_1 - \beta)(\delta)}{d^2}$$

With a statistical trust of 95% that corresponds to the type I error, and is the same as 1.96, with a potency of 80% that corresponds to the type II error, and equals to 0.84. It's considered as a standard deviation for the increase of 1.47 seconds 2 in the tear film breakup time posterior to 60 days of ciclosporin application A, with an expected difference of at least 10.2 seconds.

Based on the previous the result was of 120 cases per group, which was incremented 20% per consideration to the losses (24 cases), with a total of **144 cases per group**, with a total population of study of **288 eyes to treat**.

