14. PROPOSED STATISTICAL ANALYSIS

The statistical analysis will be performed by a researcher blinded to the intervention groups.

The continuous quantitative variables will be expressed and presented via measures of central tendencies and of dispersion (media, standard deviation and ranges).

The nominal qualitative variables and ordinals will be presented via frequencies and proportions.

The Kolmogorov-Smirnov test will be performed in order to know the normal distribution or not of the obtained results in each study group. Also, the Levene test will be performed in order to know if the variables are the same or different.

Assuming a normal distribution of the data, the intra-group differences will be determined via the t test for paired samples, in the case of the quantitative variables. For the quantitative variables the χ^2 test (chi squared) will be used and in case that the expected frequencies are less than 5 the exact Fisher test will be used.

The differences among the groups will be analyzed via the t test in case of quantitative variables. For the quantitative variables tables of contingency 2x2 will be made and the differences will be calculated via χ^2 (chi squared) with Yates correction in case that the expected frequencies are less than 5 the exact Fisher test will be used).

The level of significance will be alpha of 0.05 or less.

A final statistical analysis will be included to all the subjects that complete 3 visits in the chronogram of activities.

15. Results report

The results obtained during the development of the investigation's protocol will be the responsibility of the sponsor, who is under obligation of reporting them to the pertinent authorities. Plus each one of the participating researchers will receive a results report.

The objective is to achieve the publication of the study on an international magazine with the objective of disseminate the scientific knowledge obtained.

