16.2 Subject identification

All the subject of the study will be identified through a number and their initials.

In the scrutiny stage a number will be assigned to the participant in a consecutive manner, employing 3 digits and once included the subject will be assigned with the subject's number (CFR number) which will be conformed of 3 digits of the molecule, 2 of the center's number, and 3 digits of the consecutive number assigned at the research center.

For example:

155/01/001 (molecule number/ center's number/ subject's number at the center).

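### Both eyes of a bilateral subject count as separate cases, but section 14 has no method for fellow-eye correlation; if they share an arm, the t test exceeds its 5% error rate

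*Combined protocol and SAP*

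**What the plan says.** **Unit of analysis.** Section 7.2 lets a subject with two qualifying eyes enter both: such subjects "can participate with both eyes, taking each eye as one case". Section 12.4 counts in the same unit ("Based on the previous the result was 69 cases (eyes) per group"), adds 20% for losses, and reaches 83 per group and 166 eyes in total. It includes no design effect.

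**Unit of randomisation.** The text points two ways.
- Section 7.2 speaks of cases: "The total population will be 166 cases, which will be randomly included and distributed in 2 study groups".
- Section 7.5 speaks of persons: "The subjects are distributed into the study groups on the visit indicated in the study timetable, through simple 1:1 randomization". Section 7.3 describes blinding as a state in which the subject and physician "do not know which study subjects were assigned to which treatment group".
- Section 16.2 gives one number per person ("once included the subject will be assigned with" a single identifier). The labels in 8.1.1 and 8.1.2 have a subject-number field and no eye field. Section 16.5 refers to the bottle of each subject, and the regimens in 7.4 have no right-eye or left-eye split.

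**Analysis.** Section 14 lists Kolmogorov-Smirnov and Levene tests, then: "The differences among the groups will be analyzed via the t test in case of quantitative variables". Contingency tables get chi-squared with Yates correction, or Fisher's test. The only paired method is for change within a group: "the intra-group differences will be determined via the t test for paired samples". The significance level is 0.05.

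**Outcomes.** Sections 6 and 13 list conjunctival hyperemia, tear film breakup time and adverse events as primary. The table in 13.3 classes breakup time as continuous and hyperemia as ordinal. The OSDI in Appendix 3 yields one score per person.

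**The concern.** Two eyes of one person usually resemble each other. If both receive the same treatment, the second eye adds less information than an eye from a new person, yet the planned t test counts it in full. The standard error is then too small, and the test declares a difference more often than the stated 0.05.

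The paired t test does not help. It compares visits within an arm and leaves the between-group comparison untouched.

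Two further problems follow from the case definition:
- The number of independent people behind 166 cases cannot be recovered from the plan.
- Person-level outcomes have no stated rule. If OSDI is entered per eye, a bilateral subject's score is simply duplicated. For symptoms and adverse events the plan does not clearly say whether the count is per eye or per person.

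**Working it through.** **1. The plan's own figure.** From 69 per group, 69 × 1.20 = 82.8, rounded up to 83, and 2 × 83 = 166. The 69 itself does not reproduce. With SD 0.4 and difference 2.9, n = 2 × (1.96 + 0.84)² × 0.4² / 2.9² = 0.30, so 1 per group. With the two inputs exchanged and unrounded normal quantiles, n = 2 × 7.849 × 2.9² / 0.4² = 825.1, so 826. That is a separate problem and the check below does not depend on it.

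**2. Inputs for this check.** From the documents: 166 eyes, simple 1:1 randomisation, t test, two-sided alpha 0.05 (z = 1.96). Assumed, because the documents give neither: p, the share of eyes that come from bilateral subjects, and rho, the correlation between fellow eyes.

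**3. Formula, fellow eyes in the same arm.** Each eye of a bilateral subject has one correlated partner in its own arm. The variance of an arm mean is therefore multiplied by DE = 1 + p × rho, while the t test assumes DE = 1. Actual type I error = 2 × [1 − Φ(1.96 / √DE)]. Effective eyes = 166 / DE.

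| p | rho | DE | Type I error | Effective eyes of 166 |
|---|---|---|---|---|
| 0.1 | 0.5 | 1.05 | 5.6% | 158 |
| 0.3 | 0.3 | 1.09 | 6.0% | 152 |
| 0.3 | 0.5 | 1.15 | 6.8% | 144 |
| 0.5 | 0.5 | 1.25 | 8.0% | 133 |
| 0.5 | 0.8 | 1.40 | 9.8% | 119 |

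At the extreme, if every eye came from a bilateral subject and rho were 0.8, DE = 1.8 and the error is 14.4%.

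**4. Number of people.** At p = 0.3, about 50 eyes come from 25 bilateral subjects and 116 eyes from 116 others, so 141 people. At p = 0.5, 84 eyes come from 42 subjects and 82 from 82 others, so 124 people.

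**5. Simulation.** 20,000 trials per cell, 166 eyes, no treatment effect; Monte Carlo standard error about 0.2 percentage points.

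| Rejection rate at nominal 5% | p 0.3, rho 0.5 | p 0.5, rho 0.5 | p 0.5, rho 0.8 |
|---|---|---|---|
| t test, fellow eyes in same arm | 6.9% | 7.8% | 10.2% |
| t test, eyes randomised independently | 4.9% | 4.8% | 5.0% |
| t test, fellow eyes in opposite arms | 3.3% | 2.4% | 1.0% |
| Yates chi-squared, same arm (assumed 30% event rate) | 4.5% | 4.7% | 6.2% |
| t test on subject means, same arm | 5.0% | 4.8% | 5.1% |
| Subject-clustered standard error, same arm | 5.3% | 5.0% | 5.2% |

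The simulation agrees with the formula. The Yates test starts from about 3.4% without clustering, so correlation raises it too, but from a conservative base.

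**The case against.** The strongest objection is that same-arm allocation is an inference. The document uses the word subject loosely: in 12.4 it adds a loss of 14 subjects to 69 eyes to get 83 cases, so subject there means eye. Section 7.2 says that cases are distributed. If each eye were randomised on its own, the t test would hold its level. This stands as a limit on the inflation claim, which is conditional. It does not remove the gap, because no section states how a second eye is allocated, and the labels and regimens without an eye field still favour a shared arm.

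Second, breakup time, the clearest t-test outcome, is also listed as a safety measure in 5.1.2 and 13.2. Hyperemia, the main efficacy outcome, is ordinal in 13.3. If it goes to a 2×2 table with Yates correction, the simulated error stays below 5% in two of three scenarios. That is true. Breakup time is nonetheless a listed primary outcome. Section 12.4 also sizes hyperemia as a continuous variable, so the documents do not settle which test it gets.

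Third, the excess may be small. With few bilateral subjects it is: 5.6% at p = 0.1 and rho = 0.5. But the plan permits bilateral entry without a cap, and the direction is not in doubt for positive correlation.

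Fourth, adverse events are measured in 13.3 as a number of cases, which under 7.2 could mean eyes. That is a possible reading, not a stated rule.

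Last, the effective-eye figures start from 166 enrolled eyes, whereas the evaluable target is 2 × 69 = 138. The ratios are the same: 138 / 1.15, 138 / 1.25 and 138 / 1.40 give 120, 110 and 99.

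**Conclusion.** The concern holds. That the plan analyses two eyes of one person as independent and provides nothing for their correlation follows from the text alone. That this inflates the type I error rests on three conditions: fellow eyes share an arm (the best-supported reading), some bilateral subjects are enrolled, and fellow eyes are positively correlated. Under these conditions the t test on a primary outcome does not hold the stated 0.05. The error is about 5.6% to 10% over the main range of assumed p and rho. The true size cannot be fixed from the documents. For outcomes tested in 2×2 tables with Yates correction, any excess over 5% is smaller and may be nil. This needs correcting before analysis, because following the plan as written gives an invalid test on that reading.

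**What to change.** 1. Reconcile 7.2 with 7.5: state whether persons or eyes are randomised, and whether fellow eyes share an arm.
2. In section 14, analyse eye-level outcomes with a mixed model or GEE clustered on subject, using a form suited to ordinal data for hyperemia. Simpler options are one study eye per subject chosen by a rule fixed in advance, or the subject mean; the mean is valid only if fellow eyes share an arm.
3. Analyse OSDI and any other person-level outcome once per subject. State whether symptoms and adverse events are counted per eye or per person.
4. Report subjects as well as eyes in each arm.
5. Restate the power of 166 eyes under an assumed bilateral share and correlation, once the derivation of 69 per group has been settled.

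The cost is wording and a standard method, with no new procedures and no extra enrolment proposed. The drawback is that stated precision and power become less favourable. For scale, matching the information of 166 independent eyes would take 166 × DE eyes: 191, 208 or 233 (rounded up) at DE 1.15, 1.25 and 1.40. These are ratios only, since the 166 has no reproducible power basis. A one-eye rule also discards data.
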